Feasibility of Teleyoga for Treatment of Lyme Disease

Study Protocol and Statistical Analysis Plan

NCT #: 04867473

June 21, 2023

Background

Lyme Disease (LD) is a debilitating condition, which infects an estimated 300,000 people each year and is associated with high personal and societal costs (1). Lyme Disease is associated with many symptom sequelae, including fatigue, joint and muscle pain, and cognitive difficulties, which impact daily activities (5). In later phases, untreated LD can lead to arthritis and arthralgias, cardiac complications, and even death. Though most early phase LD patients are successfully treated with one course of antibiotics, a minority (10-20%) of those successfully treated continue to experience persistent symptoms of fatigue, depression, musculoskeletal pain, and cognitive complaints, called Post Treatment Lyme Disease Syndrome (PTLDS) (2). The efficacy of a repeat course of antibiotics has not been supported for PTLDS; rather, typical recommended treatments are cognitive behavior therapy (CBT), antidepressants, and low-impact aerobic exercise. The efficacy of these interventions appears to be limited. Consequently, an adjunct treatment to medication interventions for LD that is non-invasive, has a low side-effect profile, and is relatively easy to implement at home could address these primary complaints. Although studies have shown yoga improves symptoms of chronic pain, cognition, sleep, and mood (3), no clinical trial has examined yoga for LD. However, yoga may be valuable for treating musculoskeletal pain in LD for several reasons: First, LD patients often report reductions in daily movement and exercise (5), which yoga could address, promoting increased physical strength and stamina. Second, musculoskeletal pain and LD share a pathological overlap of emotional problems and poor cognition, both of which respond positively to yoga. Additionally, the neuropsychological burden often reported by LD sufferers as “brain fog” has not been well established, with some studies demonstrating difficulties in memory, verbal fluency, and/or executive functioning and others finding subclinical changes or failing to replicate these findings (5). To establish the cognitive status of patients reporting LD symptoms, we intend to identify and track changes in measures of memory, verbal fluency, and executive functioning.

We are conducting a feasibility study in a parent project treating Veterans with chronic pain using yoga. That study focuses on chronic musculoskeletal pain as it is the most common type of chronic pain (4) and there is strong evidence it responds well to yoga. However, people who may benefit from yoga often encounter barriers to treatment such as travel costs and time, health conditions and caregiver responsibilities. For these reasons we have focused on a way to provide yoga at home using internet-based technology (“teleyoga”). Teleyoga is an innovative, potentially effective approach for treating chronic pain but research evaluating the acceptability or efficacy of teleyoga is very limited. We suggest that teleyoga offers great potential to treat LD patients remotely. This would be a feasibility study that would be modeled on our current project. Ultimately, a larger clinical trial would be needed to compare at-home teleyoga to in-person yoga and with the inclusion of a control group of treatment as usual for LD and patients. Before such a trial can be performed, a small-scale study is needed to demonstrate feasibility of recruitment, retention, and adherence to teleyoga.

Objectives

Specific Aims and Hypothesis

Specific Aims:

1. Modify an existing teleyoga intervention to use with LD patients and address the technical challenges of at-home teleyoga.
2. Assess neuropsychological and psychological status.

Hypothesis 1: We will demonstrate feasibility by recruiting 15 LD patients over a 9-month period, in cohorts of five patients every three months, maintain a retention rate of >65%, with acceptable adherence (a priori level of $\geq 65\%$ of classes).

Treatment satisfaction will be at least neutral for all items. We do not expect any serious adverse events.

Hypothesis 2: We hypothesize patients will demonstrate relative difficulties in memory, verbal fluency and executive functioning.

Study Design

We propose to develop home-based yoga for treating LD patients using existing HIPAA-compliant telehealth software (e.g. Doxy.me) led by a certified yoga instructor.

Yoga Intervention:

We will adapt the yoga protocol from the parent award. The protocol is 12 weeks in duration, 1 class/week, class length of 75 minutes, with additional homework 15-20 mins on 5 non-class days/week. The protocol uses seated/standing/supine yoga postures, breathing, and meditation, and contains standard modifications in cases of limited mobility. Participants will also receive a homework manual describing simple and safe exercises to practice for homework. The adapted protocol would be 10 weeks in duration, to allow for recruitment intervals, but would otherwise adhere to the active award protocol.

Recruitment: For each 3-month interval we will recruit N=5 LD and PTLDS patients.

We anticipate recruitment will be via local hospitals, including Stanford, and the Johns Hopkins Lyme Disease Research Center, a research center with an online recruitment resource and ongoing clinical trials.

Baseline: Participants will complete study measures at the study site (see Assessment Materials below). We will record their phone number, physical location, and an emergency contact, which will be confirmed at each teleyoga session.

Week 1: Participants will visit the study center and will be issued an Apple iPad. They will also receive a yoga mat, yoga strap, and yoga blocks. Since the goal is to address the technical feasibility of teleyoga, this session will focus on anticipated technical issues, such as charging the iPad, connecting the iPad to home Wi-Fi, using the volume buttons, using the case as a stand, at-home lighting requirements, etc. We will also provide these instructions in a booklet. These initial steps can be performed remotely if participants cannot visit the study center.

Weeks 2-8: Study staff will call caregivers one day prior to instruction and remind them to charge their iPad and join the upcoming session. The yoga instructor providing instruction will be located at home equipped with standard audiovisual apparatus (i.e., screen size 56" x 32").

Post-Treatment: Participants will visit the study site individually to complete study measures (see "Assessment Materials" section) and provide feedback.

Statistical Plan and Data Analysis

Primary analyses will be conducted focusing on treatment satisfaction, provider suggestions, retention and adherence. Due to the very small sample size (N=15) the main analytic strategy will be descriptive statistics. We will carefully examine score distributions and

will focus on cases with negative responses for treatment satisfaction. We aim to reach at least 2 on the 5-point MDTSM scale (i.e., satisfaction is neutral or positive) for all items. For retention, we aim to retain at least 65% of all participants in the study during the 10 weeks of treatment. We expect treatment attendance to be $\geq 65\%$ for the 10 treatment sessions. For feasibility of treatment fidelity we will aim for $\geq 95\%$ of treatment components. For the outcomes that will be measured repeatedly (i.e., both at baseline and post-treatment), we will estimate how they change over time (pre to post). These results will provide preliminary data on target engagement and therefore will inform and shape the future trial in terms of elucidating the mechanism of action. For all analyses regarding changes in outcomes, we will first employ simple paired t-test (pre vs. post) given the correlation between pre and post measures. In all statistical analyses, we will focus on collecting preliminary data on clinical significance (i.e., effect size) instead of making formal inference (i.e., p-value).

Inclusion/Exclusion Criteria

Inclusion Criteria (As determined by):

- Diagnosis of probable Lyme disease
- Has not begun new pain medications or other treatments in the last month
- English literacy
- Wireless internet connection at home

Exclusion Criteria for (As determined by):

- Participation in another concurrent clinical trial
- Back surgery within the last 12 months
- Unstable, coexisting mental illness or psychiatric condition
- Active, current suicidal intent or plan
- Attended or practiced yoga ≥ 1 x in the past 12 months

Informed Consent Process

Participants will be recruited from the following sources: VAPAHCS Pain Clinic, asking VA providers to refer their patients with chronic pain, web-based advertising, local advertising, social media advertising (Facebook, Twitter and Instagram), and mass-mailings to potential participants who may meet study eligibility criteria. LD patients do not need to be veterans, but veterans with LD may be recruited by asking their VA primary healthcare provider to send a letter of invitation. These sources will result in either 1) the potential participant calling the study team or 2) with the participant's consent, the study staff contacting them directly. Study candidates will be invited to VAPAHCS for a screening visit, during which the Project Manager will obtain informed consent and review the Health Insurance Portability & Accountability Act (HIPAA) document.

1. The Project Manager will explain the information contained in the written informed consent forms (purpose, procedures, risks, benefits, alternatives to participation, etc.) and HIPAA documents to the study candidates verbally, in lay language.
 - a. The Project Manager will check for comprehension, allow the study candidates ample opportunity to ask questions throughout the process, and repeat the information, as necessary.
 - b. Care will be taken to inform the study candidate that their participation is entirely voluntary, and they may withdraw at any time and for any reason without penalty or loss of benefits to which they would otherwise be entitled.
 - c. Study candidates will then be asked to carefully read the informed consent form to consider whether or not to participate in the research and to ask questions.
 - d. To ensure that the study candidate understands the research, they will next be asked to summarize the consent form and HIPAA addendum, with a special focus on the discomforts, risks, benefits, and confidentiality sections.
2. If the study candidate demonstrates (by stating in his/her own words) an understanding of the purpose, risks, and benefits of the study and agrees to participate in the study, he/she will be asked to initial each page, in addition to sign and date the last page of the consent form and the HIPAA document.
3. The Project Manager who oriented and obtained informed consent will sign and date the informed consent form.
4. The Project Manager will provide each enrolled participant with a photocopy of the original signed copy and keep the original signed copy in a binder in a locked cabinet.

The emphasis on the voluntary nature of participation is designed to minimize the possibility of coercion or undue influence on participation. The study candidate will be given time to understand the written informed consent form and make an informed decision. All treatments for this study will be provided in group formats, so potential participants will be reminded that full anonymity cannot be maintained. Following the informed consent process, the enrolled participant will complete other measures (See Research Strategy).

Screening Procedures

Potential participants (n=15) will be screened via phone. The Project Manager will obtain informed consent and review the Health Insurance Portability & Accountability Act (HIPAA) document. After obtaining informed consent, a trained researcher will collect demographic information (Demographic Questionnaire).

Study Assessments

Assessment Materials: Demographics Questionnaire; Clinical Questionnaire; Medication Use; Yoga Home Practice Log; BDI-II Beck Depression Inventory-II (BDI-II); Patient Safety; Treatment Satisfaction: PEG; Multi-Dimensional Treatment Satisfaction Measure (MDTS); SF-36; CANTAB.

Demographics Questionnaire: Documents age, gender, education, and race/ethnicity.

Clinical Questionnaire: Self-report document focusing on the existence of 78 health symptoms taken from a list of ICD-9 codes that are highly likely to represent chronic pain.

Medication Use: Self-report of all current pharmacological and non-pharmacological treatments.

Yoga Home Practice Log: Log for participant to document their yoga home practice on non-treatment days.

BDI-II Beck Depression Inventory-II (BDI-II): Contains 21 self-report questions, scored on a 0-3 scale, related over the past two weeks to sleep, appetite, punishment, suicide, and interest in sex.

Patient Safety: Outcomes will be monitored to record the type and frequency of adverse events, as defined by standard IRB regulatory reporting requirements.

Treatment Satisfaction: Assessed using the Multi-Dimensional Treatment Satisfaction Measure (MDTSM). The measure consists of 11 subscales assessing treatment process and outcome attributes. Each subscale has 1-8 items (see Table 5). Each question except the Discomfort subscale is rated on a five-point scale ranging from “not at all (0)” to “very much (4)”. Thus, a score of 2 represents a rating of neutral satisfaction. The instrument was developed for behavioral interventions and is designed to provide a comprehensive set of treatment attributes to consider when evaluating treatments in the context of pilot studies. It is designed to be completed after exposure to an intervention, to point to aspects of treatments that are viewed favorably or unfavorably. The MDTSM is relevant to many types of behavioral interventions and can be tailored to our yoga intervention. The MDTSM subscales demonstrates good internal consistency, reliability, and validity.

PEG: A 3-item pain measure derived from the Brief Pain Inventory and validated in ambulatory care settings. It includes 1 severity item (average pain) and 2 interference items (enjoyment of life and general activity).

SF-36: Health related quality of life-short form (69): Eight scales measuring physical functioning, role limitations due to physical problems, bodily pain, general health perceptions, vitality, social functioning, role limitations due to emotional problems, and mental health.

Cambridge Neuropsychological Test Automated Battery (CANTAB): Cognitive function was measured with the Cambridge Neuropsychological Test Automated Battery (CANTAB) at baseline and end of treatment. Three tests were administered (PAL, SWM and RVP).

| | Data Collection | | | |
|-----------------------------------|-----------------|----------|-----------------|----------------|
| | Screening | Baseline | Yoga (wks 1-12) | Post-treatment |
| Background | | | | |
| Consent Form | × | | | |
| Demographic Questionnaire | × | | | |
| Clinical Questionnaire | × | | | |
| Yoga Medical Clearance Form | × | | | |
| Medical Use | | × | | × |
| Yoga Home Practice Log | | | × | |
| Mental Health | | | | |
| BDI-II | | × | | × |
| Pain/QOL/Physical | | | | |
| PEG | × | × | | × |
| Behavioral & Cognitive | | | | |
| Treatment Satisfaction | | | | × |
| Patient Safety | | | × | × |

| | | | | |
|--------|--|--|---|---|
| SF-36 | | | x | x |
| CanTab | | | x | x |

Table 1. Study Measures and Timetable of Data Collection

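### Does the target of at least 2 for all satisfaction items fail on the Discomfort subscale, which is not rated 0 to 4?

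*Combined protocol and SAP*

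**What the plan says.** Treatment satisfaction is one of the outcomes at the centre of the main analysis: "Primary analyses will be conducted focusing on treatment satisfaction, provider suggestions, retention and adherence" (Statistical Plan and Data Analysis). The target appears twice.

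- Hypothesis 1, under Specific Aims and Hypothesis, gives it in short form: "Treatment satisfaction will be at least neutral for all items".
- Statistical Plan and Data Analysis gives the numerical form: "We aim to reach at least 2 on the 5-point MDTSM scale (i.e., satisfaction is neutral or positive) for all items".

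The Treatment Satisfaction entry under Study Assessments describes the instrument. "The measure consists of 11 subscales assessing treatment process and outcome attributes". The number of items per subscale runs from 1 to 8, with a reference to a Table 5 that is not in the text available here. On scoring it says: "Each question except the Discomfort subscale is rated on a five-point scale ranging from" 0 at the lower anchor to 4 at the upper. It then concludes: "Thus, a score of 2 represents a rating of neutral satisfaction".

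The text available here gives no response range, anchors or scoring direction for Discomfort. Since Table 5 is not visible, this is not counted as an omission.

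**The concern.** The meaning of 2 as neutral is derived from the 0 to 4 rating, and the sentence that introduces that rating takes Discomfort out of it. Both statements of the target nevertheless refer to all items, and neither names an exception. Read literally, the criterion reaches items for which the document has assigned no neutral value.

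The consequence could matter because of the form of the rule. A criterion that every item must meet can be decided by a single item. One analyst might include Discomfort and another leave it out, and they could then report different answers to whether the satisfaction target was met. The plan puts effect sizes ahead of p-values, so readers are likely to judge feasibility largely by the targets set in advance. The plan also intends to look closely at negative satisfaction responses, and what counts as negative on a Discomfort item is not defined in the text either.

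**Working it through.** **Inputs**

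- Scale anchors: 0 and 4 (Study Assessments, Treatment Satisfaction).
- Subscales: 11, of which one, Discomfort, is excepted from that scale (same entry).
- Items per subscale: 1 to 8 (same entry); the count for Discomfort is not given.
- Target: at least 2, on the 5-point scale (Statistical Plan and Data Analysis).

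**The plan's own figure.** Neutral is the midpoint of the rating: (0 + 4)/2 = 2. The stated value is reproduced, and it is right for every question on that scale.

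**Reach of the cut-off.** Subscales on the 0 to 4 scale: 11 − 1 = 10. Subscales off it: 1/11 = 9.1%. The number of Discomfort items lies between 1 and 8.

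**Reading the sections together.** The rest is a matter of wording.

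1. The numerical target does not stop at all items. It places the value of 2 on the 5-point scale and explains it as neutral or positive satisfaction.
2. The instrument description identifies the questions on the five-point scale as all those outside Discomfort.
3. Taking 1 and 2 together, the items to which the target can be applied are those of the ten 0 to 4 subscales. For these, both the threshold and its meaning are defined.
4. Hypothesis 1 has no scale qualifier. It gives no number either: it asks for at least neutral satisfaction, and the only definition of neutral in the document is the one drawn from the 0 to 4 rating. The analysis section turns this short statement into an operational rule.

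**Can the plan, followed as written, give a wrong result?** For the ten subscales it cannot: the cut-off is the correct midpoint. For Discomfort, a perverse result, such as failing a participant who reports no discomfort, would require three things: that the analyst applies the cut-off outside the scale it is stated on, that higher scores mean more discomfort, and that the items are not reverse-scored. The first goes against the analysis section's own wording. The documents support neither the second nor the third, so no such result can be demonstrated from them.

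**The case for a change.** The strongest case for a change is that the limit is only implicit. The phrase naming the 5-point scale shares a sentence with the reference to all items, and Hypothesis 1 lacks the phrase altogether. Table 5 might give the Discomfort response options, but that would not by itself write an exemption into the target. Satisfaction is a named focus of the primary analyses, one item can decide an all-items rule, and a clarifying clause would cost almost nothing.

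Part of this stands. There is no explicit exemption, and a reader who had only Hypothesis 1 could not infer one. But it shows incomplete wording, not a faulty analysis. The study's analysts will have the questionnaire and its response options, so the scale and direction of the Discomfort items will not be unknown to them. The same applies to recognising a negative response on those items. The only question really open to them is whether Discomfort counts towards the target, and the analysis section's reference to the 5-point scale points to the answer.

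The stakes are also lower than a pass/fail reading suggests. The target is worded as an aim. Nothing in the plan makes a decision depend on meeting it. Score distributions are to be examined in any case, with attention to unfavourable responses, so Discomfort results would be seen whether or not they count towards the target. Adverse events are recorded separately under Patient Safety.

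**Conclusion.** The concern is accurate about the wording but does not call for a change. The cut-off of 2 is correct for the 10 subscales rated 0 to 4, and the analysis section ties the target to that scale. What is missing is an express statement that the remaining subscale (1 of 11, 1 to 8 items) falls outside the target. Analysts fill this gap sensibly by applying the target to the 0 to 4 items and describing Discomfort on its own response scale.

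This conclusion rests on two assumptions: that the 5-point scale named in the target is the five-point rating described under Study Assessments, and that those who analyse the data have the questionnaire in hand. Both are reasonable. If either failed, the effect would still be confined to how one subscale is described in a study of 15 participants that relies mainly on descriptive statistics and does not aim at formal inference.

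### Treatment satisfaction, a primary descriptive outcome, is scheduled only at the post-treatment visit, with no planned collection from people who leave the study

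*Combined protocol and SAP*

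**What the plan says.** Statistical Plan and Data Analysis gives satisfaction primary status: "Primary analyses will be conducted focusing on treatment satisfaction, provider suggestions, retention and adherence". The target is "We aim to reach at least 2 on the 5-point MDTSM scale", for all items, and the same section says unfavourable satisfaction ratings will be looked at closely. Study Assessments describes the instrument: "Each question except the Discomfort subscale is rated on a five-point scale", running from 0 to 4 with 2 as neutral. On timing it says: "It is designed to be completed after exposure to an intervention, to point to aspects of treatments that are viewed favorably or unfavorably". Finishing the course is not made a condition, and no minimum number of classes is given.

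Table 1 gives "Treatment Satisfaction" a single mark, in the post-treatment column. Study Design places that assessment: "Post-Treatment: Participants will visit the study site individually to complete study measures". A remote alternative is stated only for the Week 1 set-up: "These initial steps can be performed remotely if participants cannot visit the study center".

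The retention target is more than 65% in Hypothesis 1 and at least 65% in Statistical Plan and Data Analysis, counted over the ten treatment weeks. Informed Consent Process allows withdrawal at any time. The available text describes no exit assessment, no analysis set for satisfaction and no rule for missing ratings.

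**The concern.** The plan says it will look hardest at unfavourable ratings. People who try the classes and then leave the study are a likely source of such ratings, and the schedule has no point at which they would be asked. Reporting retention shows how many left, but not how they rated the programme or what they disliked.

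The study exists to inform a larger trial. If leavers are less satisfied than those who stay, that trial is designed on a picture of acceptability that is too favourable. Whatever the direction of any bias, feedback from leavers that could be used to adapt the intervention is lost.

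**Working it through.** **Inputs.** From the documents: 15 participants, the 65% retention target, the 0–4 scale with neutral at 2, and one satisfaction assessment at post-treatment. The documents give no expected scores or dropout reasons, so every score, negative-response rate and number of absentees below is assumed. The figures apply to items on the 0–4 scale, that is, all but the Discomfort subscale. The plan has no figure of its own to reproduce.

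**Step 1: how many can be lost with the retention target met.** 0.65 × 15 = 9.75, so 10 must be retained. 10/15 = 66.7% meets both wordings; 9/15 = 60.0% meets neither. Up to 5 can leave.

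**Step 2: who is missed.**
- Stops attending classes but stays in the study: still due at the post-treatment visit, so covered.
- Leaves the study: no planned contact, so missed.
- Retained through the ten weeks but unable to attend the visit: missed, because no remote option is stated for these measures.

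Five is therefore not a cap on missing ratings. There are more if retained participants miss the visit, and fewer if some leavers are assessed anyway.

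**Step 3: if the target is a mean per item.** Let N be class attenders, L those without a rating, m the respondent mean and d the mean of those missing.

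- Mean over all attenders = ((N − L)m + Ld)/N
- Overstatement = m minus that mean = (L/N)(m − d)
- Value of d below which the overall mean falls under 2 = (2N − (N − L)m)/L

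With m = 2.3:

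| Scenario | L/N | Mean if d = 1.0 | Mean if d = 2.0 | Mean falls under 2 if d is below |
|---|---|---|---|---|
| Five leavers, all had attended a class | 5/15 = 0.33 | (23 + 5)/15 = 1.87 | (23 + 10)/15 = 2.20 | (30 − 23)/5 = 1.4 |
| Two of the five left before any class | 3/13 = 0.23 | (23 + 3)/13 = 2.00 | (23 + 6)/13 = 2.23 | (26 − 23)/3 = 1.0 |
| Five leavers and two retained absentees, all seven alike | 7/15 = 0.47 | (18.4 + 7)/15 = 1.69 | (18.4 + 14)/15 = 2.16 | (30 − 18.4)/7 = 1.66 |

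If all five left before any class, they cause no bias among attenders. If the two absentees rate like respondents, the overstatement stays at 0.33 of the respondent-leaver difference.

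With 5 of 15 missing, the threshold for d is (30 − 10m)/5:
- m = 2.1: 1.8
- m = 2.5: 1.0
- m = 3.0: 0

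On a mean rule with five missing, no reversal is possible once respondents average 3.0.

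**Step 4: if the target applies to each rating.** The respondent mean then gives no protection. Take ten respondents all scoring 3 and one leaver scoring 1: the mean over the eleven is (30 + 1)/11 = 2.82, yet the item fails.

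If none of 10 respondents scores below 2, the proportion below 2 among all 15 lies anywhere from 0/15 = 0% to 5/15 = 33.3%.

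As an illustration for one item, assume independent ratings, a 10% chance of a rating below 2 in each respondent, and 30% to 50% in each leaver. The chance of seeing no such rating is:
- among 10 respondents: 0.9^10 = 35%
- among all 15, leavers at 30%: 0.349 × 0.7^5 = 6%
- among all 15, leavers at 50%: 0.349 × 0.5^5 = 1%

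**The case against.** The strongest reply is that this caution applies to any end-of-treatment questionnaire. The study is a single group of 15, is descriptive and disclaims formal inference. Retention is reported beside satisfaction, so losses are visible. Nothing shows that leavers are less satisfied; they may leave for health, travel or time reasons. Ratings after one class and after ten weeks also measure somewhat different things.

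Much of this stands. The direction of bias is an assumption, no error rate or sample size is affected, and early and late ratings should not simply be pooled. But a retention count does not replace the missing ratings, and satisfaction is a primary outcome with its own target.

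Four stronger readings are tempting, and the documents do not support them:

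- A reader might infer that only people who complete the classes are rated. The plan separates retention in the study from class attendance, and the post-treatment visit has no attendance condition, so low attenders who stay are covered.
- A reader might infer from the Background that the site visit itself will lose people, since it says "people who may benefit from yoga often encounter barriers to treatment such as travel costs and time, health conditions and caregiver responsibilities". That passage is about barriers to treatment and argues for yoga at home; it says nothing about a single assessment visit. The case for a remote option rests on the schedule alone.
- A reader might infer that a wrong pass can arise only when ratings are near neutral. That holds on a mean rule, which the plan does not state.
- A reader might infer that exit or remote collection is ruled out. It is not forbidden; it is unplanned in the text available. Consent pages are not available, and Informed Consent Process refers to a Research Strategy that is not included.

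**Conclusion.** The point holds as a gap in planned data collection for a primary descriptive outcome. The plan can meet its retention target with 5 of 15 people lost and never asked about satisfaction. The result is too favourable only if leavers are less satisfied, which the documents neither state nor exclude.

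The size depends on a rule the plan leaves open. On a mean rule the overstatement is one third of the respondent-leaver difference with 5 of 15 missing (range 0 to 0.47 across the assumed scenarios), and a changed conclusion needs near-neutral respondents and clearly less satisfied leavers. On an individual-rating rule a single leaver's rating below 2 changes the result for an item that respondents alone would pass. On either rule the leavers' feedback is lost. This is a worthwhile, inexpensive improvement and not a flaw that invalidates the study.

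**What to change.** **Collection.** Add an early-withdrawal entry to Table 1: offer the MDTSM by phone or online, with the reason for leaving, to anyone who withdraws after at least one yoga class (the Week 1 technical session alone does not count). Keep it optional, consistent with the right to withdraw. Allow remote completion for retained participants who cannot attend the post-treatment visit.

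**Analysis.** State whether the target of 2 applies to the item mean or to each rating. Report early-withdrawal ratings separately from end-of-treatment ratings, and also combined. Give the number of respondents out of class attenders and out of all enrolled. For each item on the 0–4 scale, show the number scoring below 2 beside the number missing. Label any mean-based pass/fail or tipping-point figure as conditional on a mean rule. If collection has already ended, these reporting changes can still be made.

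**Cost.** One optional contact per person who withdraws after a class (at most five if the retention target is met), a remote option for any retained absentee, existing staff, a short addition to the analysis text and possibly one line in the consent form.

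**Downsides.** Some leavers will not respond. Outcome items may be hard to rate after few classes. The form may be long: with 11 subscales of 1 to 8 items, the total is 18 (10 × 1 + 8) to 81 (10 × 8 + 1) if both extremes occur. Remote and site ratings may differ slightly, and reported satisfaction may be less favourable.
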